## 7. DATA MANAGEMENT, PRESENTATION, AND ANALYSIS CONSIDERATIONS

### 7.1 Programming Environment

SAS® version 9.4 or higher (SAS Institute, Cary, North Carolina) will be used for statistical analyses and the production of tables, figures, and listings (TFLs).

### 7.2 Tables, Figures, and Listings

Tables of contents for TFLs to be produced are shown in [Appendix B](#). All TFLs will be appended to the final CSR.

#### 7.2.1 Tables and Figures

- Tables and figures will present data summaries and/or analyses for the appropriate study population; e.g., summaries of safety parameters will be shown for the safety population only.
- Treatment group order in tables and figures will be usual care, CAP-1002, and “All Subjects.” Note: not all tables and figures will show data summarized for “All Subjects.”
- Tables and figures will present summaries/analyses by study visit window, if applicable.
- Table column headers and figure legends will include subgroup sample sizes.

#### 7.2.2 Listings

- Listings will present all data collected for all subjects unless the listing applies only to a specific analysis population (e.g., a listing of treatment-emergent AEs applies only to the safety population).
- Listings will be ordered by unique subject identifier, study visit window (see [Section 7.7](#)), date, and data collection time.

### 7.3 Data Analysis

- The anchor date used for summaries and analyses will depend on the analysis population, as follows:
  - ITT population: randomization date
  - mITT population: IP administration or reference date

- Safety population: IP administration or reference date
- Per protocol population: IP administration or reference date
- Categorical variables will be summarized as frequencies and percentages in each category. Percentages will be reported to one decimal place. Unless otherwise noted in Sections 8-10, categorical variables will be analyzed using chi square tests of association or, if any contingency table cell has less than 5 subjects, Fisher's exact test.
- Continuous variables will be summarized by numbers of subjects, means, standard deviations, medians, and ranges. The number of decimal places for minimums and maximums will be the same as the original data. The number of decimal places for means, medians, and interquartile ranges will be the same as the original data plus one. The number of decimal places for measures of variance will be the same as the original data plus two. Unless otherwise noted in Sections 8-10, continuous variables will be analyzed using t-tests or, if appropriate, analysis of covariance with baseline as a covariate. Non-parametric tests and data transformations will be considered for variables with distributions that violate parametric assumptions.
- Data with qualifiers (e.g., “<”) will be listed with but summarized without the qualifier.
- P-values will be presented to two decimal places if  $> 0.01$ , to three places if  $< 0.01$  but  $> 0.001$ , and to four places if  $< 0.001$  but  $> 0.0001$ . P-values  $< 0.0001$  will be presented as “ $< 0.0001$ .”
- Statistical tests will be two-sided and tested at the 0.05 significance level unless otherwise noted in Sections 8-10.
- It is understood that statistical non-significance is not an indicator of equivalence.

#### 7.4 Subgroups

Differences in safety and/or efficacy by subgroups defined by the following classifiers may be explored as part of the final analysis:

- Ambulatory vs. non-ambulatory
- LVEF:  $\geq 55\%$  vs.  $< 55\%$
- Initiation of eteplirsen while on trial
- Baseline DSA MFI  $< 500$  vs. 500-1000 and/or DSA quartiles
- Donor, stromal cell derived factor 1 (SDF1) level of lot received, master cell bank, and/or other identified measures of potential cell potency

In addition, differences in safety and/or efficacy based on exposure to various heart failure medications, such as mineralocorticoid receptor antagonist (MRA), may be explored.

#### 7.5 Missing Data

- Listings will present data as reported.
- Missing or partially missing dates that are required for date-dependent definitions (e.g., treatment-emergent AEs, concomitant medications) will be assumed to be the most conservative date possible. For example, an AE with a completely missing start date will

be considered treatment-emergent; similarly, an AE that started the same month and year as IP administration but with missing start day will be considered treatment-emergent.

- Handling of missing endpoint data in summaries and analyses for each endpoint is described in Sections 8-10.

## 7.6 Study Period and Time Point Definitions

The following study periods and time points are defined:

Screening Period: the 30-day time period before IP infusion or the reference time point.

Baseline: for a given parameter for a given subject, the last observation before IP infusion or the reference time point.

Day 0: for a given subject, the day of planned IP infusion or the reference day.

(Nominal Visit) Analysis Time Point: analysis based on data collected at the *(nominal visit)* time point, where nominal visits are as shown below in [Section 7.7](#).

End of Study (EOS), Subject Level: subject-level EOS is reached after completion of the Month 12 visit or discontinuation for any reason.

EOS, Study-Level: EOS is reached when all randomized subjects have either completed the Month 12 visit or have discontinued from the study for any reason.

Long-Term Follow-Up (LTFUP) Period, Subject-Level: the LTFUP period begins after completion of the Month 12 visit and continues until 4 more annual visits have been completed.

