### **6.5.2 Sample Collection, Storage, and Shipping**

All clinical laboratory testing in this trial will be performed by central laboratory facilities, except those performed on Days 0 and 1 for subjects randomized to CAP-1002 only. All samples will be collected, processed, stored and shipped (as applicable) according to instructions in the Clinical Laboratory Manual for this trial.

For subjects randomized to CAP-1002, the clinical site should collect and process samples for the following tests in accordance with their institutional policies to appropriately monitor subject safety pre and post infusion:

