**Table 2. Local Laboratory Testing, Day 0 and Day 1 (CAP-1002 Arm Only)**

Pre-Infusion	Post-Infusion
Troponin I	Troponin I ( serial collection )
CK-MB	CK-MB ( serial collection )
Serum Chemistry*	Serum Chemistry*
Hematology*	Hematology*
Urinalysis*	Urinalysis*
PTT & INR (if taking warfarin)	

\*See Appendix 2 for details

Serum for the donor specific antibody (DSA) monitoring, HLA typing and blood for the ELISpot assay will be collected and processed at each site and then shipped to a central core laboratory for analysis within 24 hours of obtaining the specimens (See Laboratory Manual for shipping instructions). Subjects will be monitored for the development of a cellular immune response using the ELISpot (enzyme-linked immunosorbent spot) assay. The ELISpot assay will be performed at screening and at the Week 6 study visit.

Serum for research purposes (biomarkers) will be collected and processed at each site then shipped to a central core lab that will then ship to Capricor for final storage and analysis (if subject has provided consent).

For subjects who provide consent and/or assent, serum for clinical research into biomarkers will be collected at every scheduled visit (excluding infusion) and sent to the Sponsor, or designee, for storage and/or analysis (including and future analysis). Per the Code of Federal Regulations (21 CFR 320.38), serum samples collected from study subjects will be maintained in storage for at least five (5) years following the date on which the IND application or supplemental application is approved. If such application or supplemental application is not approved, serum samples will be maintained in storage for at least 5 years following the date of completion of the clinical research study.

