### 7.1 Screening Visit

Written informed consent or assent must be obtained from the subject prior to performing any study-related tasks. Afterwards screening period for that subject will begin and the following screening procedures will be performed (not more than 30 days prior to randomization):

- Review of Inclusion / Exclusion Criteria (Section 4.2 and Section 4.3)
- Collection of demographic information
- Review of medical and cardiac history, and concomitant medications
- Measurement of vital signs (body temperature, HR, BP, and RR), weight and height
- 12-lead ECG
- 24-hour ECG via sponsor-provided continuous cardiac rhythm monitoring system
- Cardiac and limited physical examination
- Cardiac MRI
- Venous blood will be collected for the following:
  - Clinical laboratory tests: serum chemistry, hematology, and serology (HbsAg, anti-HCV, anti-HIV 1/2), Cystatin C, Troponin and CK-MB
  - Biomarkers: Osteopontin, ST2, IL-10, and Galectin-3
  - Exploratory biomarkers (if consent/assent provided)
  - Immunoassay: HLA, DSA, and ELISPOT
  - See 6.5 for additional information on clinical laboratory testing.
- A urine sample will be collected for urinalysis
- PUL Scale
- 6MWT (if capable)
- Pediatric QoL Inventory (PedsQL)
- PODCI
- Spirometry
- Adverse Event Assessment
- Submission of historical cardiac MRI

Subjects must continue to meet all of the inclusion and none of the exclusion criteria before proceeding to randomization. Subjects who do not proceed to randomization for any reason during screening will be withdrawn from the study as screen failures and will have no further follow up.

## 7.2 Randomization, Day 0, and Day 1

Subjects that continue to meet eligibility will be randomized (1:1) to either the active treatment arm (CAP-1002) or usual care arm.

For subjects that are randomized to the usual care arm, Day 0 will be defined as seven (7) days after the date of randomization. For subjects that are randomized to the active treatment arm, Day 0 will be defined as the date of the intracoronary infusion of CAP-1002.

**For subjects randomized to CAP-1002 only**, the infusion visit will include tests and assessments as described below and in accordance with the site's standard operating procedures.

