#### 9.5.3 Laboratory Evaluations

Laboratory values at each collection time will be listed and summarized using descriptive statistics. Each post-treatment laboratory value will be compared to baseline (last value prior to starting treatment).

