## Appendix 1 Schedule of Events

Procedure / Event	Screening	Infusion (CAP-1002 only) 		Day 1 (Home)	Day 3 (Phone)	Week 2	Week 6	Month 3	Month 6	Month 12	Early Termination 
Study Day	≤30 days prior to randomization	Day 0		Day 1 	Day 3 (+3)	Day 14 (±3)	Day 40 (±7)	Day 90 (±7)	Day 180 (±14)	Day 360 (±30)	As Needed
		PRE	POST								
Informed Consent	X										
Eligibility Assessment	X	X									
Demographics	X										
Medical History	X	X									
Cardiac History	X	X									
Concomitant Medications	X	X	X			X	X	X	X	X	X
Vital Signs	X	X	X			X	X	X	X	X	X
Weight	X								X	X	X
Height 	X						X	X	X	X	X
12-Lead ECG	X	X	X			X	X	X	X	X	X
Limited Physical Examination	X									X	X
Cardiac Physical Examination	X	X	X			X	X	X	X	X	X
Cardiac MRI	X								X	X	X
Continuous cardiac rhythm monitoring	X			X			X		X	X	X
Clinical Laboratory Tests (includes Chemistry, Hematology, Urinalysis)	X	X	X			X	X	X	X	X	X
Serology 	X										
Osteopontin	X					X	X	X	X	X	X
ST2	X					X	X	X	X	X	X
IL-10	X					X	X	X	X	X	X
Galectin-3	X					X	X	X	X	X	X
Exploratory Biomarkers	X					X	X	X	X	X	X

Procedure / Event	Screening	Infusion (CAP-1002 only) 		Day 1 (Home)	Day 3 (Phone)	Week 2	Week 6	Month 3	Month 6	Month 12	Early Termination 
Study Day	≤30 days prior to randomization	Day 0		Day 1 	Day 3 (+3)	Day 14 (±3)	Day 40 (±7)	Day 90 (±7)	Day 180 (±14)	Day 360 (±30)	As Needed
		PRE	POST								
HLA	X										
DSA	X					X	X	X	X	X	X
ELISpot	X						X				
PUL scale	X						X	X	X	X	X
6MWT	X						X	X	X	X	X
Pediatric QL Inventory	X						X	X	X	X	X
PODCI	X						X	X	X	X	X
Spirometry	X						X	X	X	X	X
Coagulation		X									
Serum Troponin & CK-MB	X	X	X			X			X	X	X
Intracoronary Infusion			X								
Adverse Event Assessment	X	X	X		X	X	X	X	X	X	X

 Day 0 is the infusion date for subjects randomized to CAP-1002. All items listed for Infusion visit and assessments on Day 0 are only applicable for subjects randomized to CAP-1002. Subjects randomized to Usual Care do not have a Day 0 visit.

 Early Termination Visit procedures to be completed at time of withdrawal, should subject be withdrawn before Month 12 Visit. A Cardiac MRI will be conducted provided the subject's most recent study-related Cardiac MRI was conducted at least three months (i.e., 12 weeks) prior to the Early Termination Visit.

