### **9.4 Safety Laboratory Evaluations**

Specific laboratory evaluations to be performed are detailed in Appendix 2 of the protocol. Listings of safety laboratory evaluations will include study visit, date and time of collection, normal ranges, observed values with out-of-range values flagged, and changes from baseline. Separate series of listings will show out-of-range observations.

Observed values and changes from baseline will be summarized by study visit. A separate series of summaries will show incidence of out-of-range observations by study visit. Shift tables will summarize shifts from one out-of-range category at baseline to another out-of-range category at each subsequent study visit and will include p-values for treatment group differences.

Listings and summaries will be done separately for each of the following laboratory evaluations or groups of evaluations:

- Serum chemistry (basic metabolic and comprehensive hepatic panels)
- Hematology
- Urinalysis
- Glycosylated hemoglobin (HbA1c)
- Cardiac (troponin I, troponin T, CK-MB)
- Immunogenicity (HLA, DSA, enzyme-linked immunosorbent spot (ELISPOT))
- Exploratory biomarkers, if available

For DSA, the raw data will be provided by the core laboratory and a listing of HLA antibodies and specific alleles will be provided to the independent clinical immunologist to make the final determination of which are DSA caused by sensitization to the donor cells, and which are non-specific changes that are not due to donor-specific sensitization. Any summary tables or analyses of DSA will be based on DSA as adjudicated by the independent clinical immunologist.

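### The last-observation baseline rule gives CAP-1002 a local-laboratory Day 0 baseline and usual care a central-laboratory screening baseline, so laboratory and baseline age are confounded with arm

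*SAP*

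**What the plan says.** **Baseline rule.** SAP 7.6 sets "Baseline: for a given parameter for a given subject, the last observation before IP infusion or the reference time point". Protocol 9.5.3 agrees: "Each post-treatment laboratory value will be compared to baseline (last value prior to starting treatment". Neither names a laboratory or a visit.

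**Which laboratory.** Protocol 6.5.2 has all clinical laboratory testing "performed by central laboratory facilities, except those performed on Days 0 and 1 for subjects randomized to CAP-1002 only". Protocol Table 2 lists the local pre-infusion tests: troponin I, CK-MB, serum chemistry, hematology and urinalysis, plus coagulation for subjects on warfarin.

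**Which samples exist.** Protocol 7.1 schedules screening blood in every subject: "Clinical laboratory tests: serum chemistry, hematology, and serology (HbsAg, anti-HCV, anti-HIV 1/2), Cystatin C, Troponin and CK-MB". Urinalysis is a separate item at the same visit. Protocol 7.2 adds the pre-infusion Day 0 samples for CAP-1002 only. A footnote to protocol Appendix 1 states: "Subjects randomized to Usual Care do not have a Day 0 visit".

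**How baseline is used.** Changes in laboratory values are a safety measure in protocol 9.5.1 and SAP 2.3.1. SAP 9.4 summarizes change from baseline by visit and plans tables of shifts from baseline "at each subsequent study visit and will include p-values for treatment group differences". The general rule in SAP 7.3 is that "continuous variables will be analyzed using t-tests or, if appropriate, analysis of covariance with baseline as a covariate".

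**The concern.** The rule is worded identically for both arms but selects different kinds of sample, because only one arm has a Day 0 draw and that draw goes to a different laboratory. Any systematic difference between local and central assays, and any effect of a same-day rather than weeks-old baseline, then appears as a treatment difference in laboratory change.

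Safety is the primary objective and the arms are small. If local laboratories read high relative to the central one, CAP-1002 baselines are inflated and new high values after treatment are under-counted in the shift tables. If they read low, spurious shifts appear. Randomization does not protect against this, because the difference is created after assignment by the sampling schedule.

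**Working it through.** The plan states no figure on this point, so there is nothing to reproduce. The check traces the rule through the schedule and then illustrates sensitivity.

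**Step 1. Apply the rule to each arm**, using protocol 6.5.2, 7.1, 7.2, Table 2 and Appendix 1.

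| | CAP-1002 | Usual care |
|---|---|---|
| Last value before infusion or reference time | Day 0, pre-infusion | Screening |
| Laboratory for that value | Local | Central |
| Baseline age at Day 0 | 0 days | 0 + 7 = 7 to 30 + 7 = 37 days |
| Laboratory, Week 2 to Month 12 | Central | Central |
| Change from baseline | Central minus local | Central minus central |

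The baseline age for usual care comes from screening at most 30 days before randomization and a reference day 7 days after it.

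**Step 2. Look for a rule that repairs this.** SAP 7.7 prefers the central result only when results from different laboratories share the same time point. A Day 0 local value and an earlier screening value do not. SAP 15 lists only the change to the mITT population.

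**Step 3. Check the enzyme schedule.** Protocol Appendix 1 has troponin and CK-MB at screening. SAP Appendix A does not; read alone, it leaves usual care with no enzyme baseline. Item 5 of SAP 2.3.1 also mentions enzyme levels on the reference date, when no usual-care sample is scheduled.

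**Step 4. Illustrate sensitivity.** Assumptions: n = 12 per arm (SAP 4), two-sided 5% level (SAP 7.3), no true effect, and a local-minus-central offset *b* added to CAP-1002 baselines only, in units of the SD of the change. The size of *b* is assumed throughout.

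*t-test on change.* Noncentrality is b × √(n/2) = b × √6, with df = 2 × 12 − 2 = 22.

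| b | Noncentrality | Rejection rate |
|---|---|---|
| 0.25 | 0.61 | 9.0% |
| 0.5 | 1.22 | 21.6% |
| 1.0 | 2.45 | 64.9% |

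*ANCOVA on baseline* (20,000 simulations). Adjustment removes only part of the bias, because the treatment estimate is still shifted by about r times the offset, where r is the assumed baseline–follow-up correlation.

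| b | r = 0.5 | r = 0.7 | r = 0.9 |
|---|---|---|---|
| 0.25 | 6.0% | 7.3% | 7.9% |
| 0.5 | 9.6% | 13.5% | 18.6% |
| 1.0 | 22.2% | 36.7% | 53.9% |

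*Offsets differing by site* (SD 0.5, r = 0.7; 3, 6 or 9 sites assumed). With mean zero, the t-test rejects 9.0%, 6.6% and 5.7%. With mean 0.5, it rejects 23.6%, 21.8% and 20.1%, and ANCOVA 14.3%, 12.9% and 12.5%.

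*Shift tables* (r = 0.7, 6,000 simulations, one common upper limit with 20% of values above it). The entries are the share of subjects moving from not high to high.

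| b | CAP-1002 | Usual care |
|---|---|---|
| +0.5 | 5.1% | 8.5% |
| +1.0 | 2.4% | 8.7% |
| −0.5 | 12.4% | 8.6% |
| −1.0 | 15.7% | 8.8% |

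Over all scenarios tried, including a limit with 50% of values above it and shifts in either direction, the Fisher test rejected at most 11.5%. When each laboratory's limit moves with its offset, the rates are 8.8% and 8.9%: no distortion.

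**Step 5. Check the remedy.** With central screening values as baseline in both arms, a local offset no longer enters the comparison. The simulated rejection rate is then 5.0% to 5.3%.

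**The case against.** - **The larger figures are for tests SAP 9.4 does not name.** It attaches p-values only to the shift tables, where the illustrated rejection rate stays below 12%. The t-test and ANCOVA come in through the general default in SAP 7.3. This stands as a limit on importance. But the shift rates themselves are distorted under a common range, and SAP 9.4 does not say whose range classifies a value.
- **A common offset in one direction at every site is a strong assumption.** This stands. With zero-mean offsets the t-test rejects only 6% to 9%.
- **Other outputs avoid baseline.** SAP 9.4 also plans observed values and out-of-range incidence by visit, which are central in both arms from Week 2, and clinically significant abnormalities are recorded as AEs. This stands, so a real signal need not be lost. It does not make the change-from-baseline comparison valid.
- **The p-values are descriptive.** Twelve chemistry and five basic hematology items at five visits make (12 + 5) × 5 = 85 comparisons, of which 85 × 0.05 ≈ 4 would be positive by chance if all were tested. That is true, but multiplicity adds noise, whereas a common offset pushes in one direction.
- **Cystatin-based eGFR may escape.** Cystatin C is not itself listed on Day 0. Table 2, however, refers to Appendix 2, which places that eGFR under serum chemistry, so its status is unclear.
- **The last value before treatment is a conventional baseline and closest to exposure.** That is reasonable when both arms are sampled alike. Here they are not.

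**Conclusion.** The concern holds. Followed as written, the plan confounds laboratory source and baseline age with arm for chemistry, hematology, urinalysis, troponin I and CK-MB at the scheduled visits from Week 2 on. That conclusion rests on the documents alone.

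The size of the bias is unknown. A common offset of half an SD of the change would raise the false-positive rate from 5% to about 22% for a t-test on change, or 10% to 19% for ANCOVA. It would cut apparent new-high shifts in CAP-1002 to about 5%, against 8.5% in usual care, if one range serves both laboratories. Zero-mean site offsets, or ranges that move with each laboratory, leave little or no distortion.

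Not affected are the CAP-1002 Day 0–1 series (local minus local), DSA, ELISpot, the four named biomarkers, adjudicated events and AE tabulations. This is a change that should be made because it is nearly free, not a threat to the main safety conclusions.

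**What to change.** 1. In SAP 7.6 and 9.4 and protocol 9.5.3, define baseline for between-arm laboratory analyses at Week 2 to Month 12 as the last central-laboratory value before Day 0, which is the screening value, in both arms.
2. Use the local pre-infusion Day 0 value only as the reference for the CAP-1002 Day 0–1 series, reported for that arm alone. SAP Appendix B already plots cardiac biomarkers in these two separate series.
3. State in SAP 9.4 which laboratory's reference range classifies each value in the shift tables.
4. Add screening troponin and CK-MB to SAP Appendix A to match protocol Appendix 1.
5. In item 5 of SAP 2.3.1, delete the closing mention of the reference date.

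The cost is about two sentences in the SAP, a matching edit in the protocol, one table row and four deleted words. No new samples are needed. Protocol Appendix 6 gives supplying a baseline for later assessments as the reason for adding screening troponin and CK-MB, so the change fits that purpose. The downsides are an older CAP-1002 baseline, as usual care already has, and two reference values per analyte in that arm. A small timing difference can remain where the infusion does not fall exactly 7 days after randomization.

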### 9.3 Analysis Populations

- **Intent to Treat (ITT) Population**: All subjects randomized. Subjects will be summarized and analyzed per their randomization assignment, regardless of the treatment (CAP-1002 or usual care) actually received.
- **Modified ITT (mITT) Population**: Subjects in the CAP-1002 treatment group who received the IP, and all subjects in the usual care treatment group who remain on study as of 9:00 am (subject's time zone) on Day 0. Subjects will be summarized and analyzed per their randomization assignment, regardless of the treatment (CAP-1002 or usual care) actually received.
- **Per Protocol Population**: Subjects with no major protocol violations. The list of subjects with major protocol violations will be compiled prior to database lock.
- **Safety Population**: Subjects randomized to CAP-1002 treatment who received the IP, and all subjects in the usual care treatment group who remain on study as of 9:00 am (subject's time zone) on Day 0. Subjects will be summarized and analyzed per treatment actually received, regardless of their randomization assignment.

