## 6. ANALYSIS POPULATIONS

The following analysis populations are defined for the trial:

**Safety Population:** Subjects randomized to CAP-1002 treatment who received the IP on Day 0, and all subjects in the usual care treatment group who remain on study as of the reference time point. Subjects will be summarized and analyzed per treatment actually received, regardless of their randomization assignment.

Intent to Treat (ITT) Population: All subjects randomized. Subjects will be summarized and analyzed per their randomization assignment, regardless of the treatment (CAP-1002 or usual care) actually received.

Modified ITT (mITT) Population for Efficacy Parameter X: Subjects in the safety population who have at least one post-baseline observation for Parameter X. Subjects will be summarized and analyzed per their randomization assignment, regardless of the treatment actually received.

Per Protocol Population: Subjects with no major protocol violations. The list of subjects with major protocol violations will be compiled prior to database lock.

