## 7.7 Visit Windows

Study visits will include Screening, Day 0, and nominal week or month indicated in the table below. Visit windows will be used in data listings, summaries and analyses and will be based on study day of the observation, defined as:

$$\text{study day} = \text{date of observation} - \text{Day 0 date}$$

Visit windows per protocol and to be used in listings, summaries and analyses are as follows:

Nominal Visit	Nominal Day	Min Day Per Protocol	Max Day Per Protocol	Min Day for Analyses	Max Day for Analyses
Week 2	14	11	17	1	29
Week 6	42	33	47	30	61
Month 3	90	83	97	62	153
Month 6	180	166	194	154	275
Month 12	360	330	390	276	427

where cell entries are study days as defined above. For example, per protocol the Month 3 visit will occur between 83 and 97 days post infusion (Day 0), but for purposes of listings, summaries

and analysis all observations dated between 62 and 153 days post infusion will be included in the Month 3 visit window.

Efficacy assessments that occur too late to be included in the Month 12 analysis window will be included in “last observation” analyses (see [Section 10](#)).

For ITT summaries and analyses, study day will be defined as:

$$\text{study day} = \text{date of observation} - \text{randomization date} - X$$

where X is the number of days between randomization and Day 0.

For example, for a subject who received IP 5 days after randomization and who had an assessment 65 days after randomization, the study day for that assessment would be 60 and the assessment would therefore fall into the Week 6 analysis window.

In addition, visit windows based on time of data collection will be defined for assessments done during the 24 hours post IP administration as follows:

Nominal Visit	Nominal Hour	Min Hour for Analyses	Max Hour for Analyses
8 Hours Post	8	4.01	12.00
16 Hours Post	16	12.01	20.00
24 Hours Post	24	20.01	28.00

If multiple valid, non-missing observations exist within a given window, the observation to be used will be:

1. the observation closest to the nominal visit day in question, or
2. the latest observation if the multiple observations are equidistant from the nominal visit day, or

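### SAP 7.6 ties Day 0 to the planned infusion day and SAP 6 requires receipt of the IP on Day 0; read literally, this could leave an infused subject whose infusion was moved out of the Safety and mITT sets

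*SAP*

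**What the plan says.** **SAP.** Section 7.6 gives Day 0 as "for a given subject, the day of planned IP infusion or the reference day". The active-arm part of the Safety Population in Section 6 is "Subjects randomized to CAP-1002 treatment who received the IP on Day 0"; usual care subjects enter by still being on study at the reference time point. The mITT for a given parameter is "Subjects in the safety population who have at least one post-baseline observation for Parameter X", so it inherits the active-arm condition. Section 7.7 computes study day as observation date minus Day 0 date.

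**Protocol.** Section 7.2 states that for the active arm "Day 0 will be defined as the date of the intracoronary infusion of CAP-1002". Footnote 1 to the Schedule of Events agrees: "Day 0 is the infusion date for subjects randomized to CAP-1002". Section 9.3 sets the Safety Population as "Subjects randomized to CAP-1002 treatment who received the IP, and all subjects in the usual care treatment group who remain on study" at the Day 0 reference time, with no condition on the day of infusion. Its mITT likewise needs only receipt of the IP in the active arm.

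**Declared differences.** SAP 15 lists one departure from the protocol's statistical methods: the requirement for a post-baseline observation in the mITT, whose new definition rests on the Safety Population. It lists neither the planned-day definition of Day 0 nor the Day 0 condition added to the Safety Population.

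**The concern.** The two SAP phrases act together. With the protocol's Day 0, requiring receipt of the IP on Day 0 excludes nobody, because every infused subject is infused on his Day 0. Once Day 0 is the planned day, the same words become a filter on treated subjects.

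Safety is the primary objective, the Safety Population carries the primary safety analysis, and there are about 12 subjects per arm. Losing a treated subject, with any event he had, would matter. A subject kept in another analysis set would have his day-based visit windows counted from the wrong origin. If the wording stays open until database lock, someone must decide who counts as treated after the data have been seen.

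**Working it through.** **Inputs.** About 12 subjects per group (SAP 4); exact 90% CIs for the composite event and its components (SAP 9.1); analysis windows of days 1–29 for Week 2, 30–61 for Week 6 and 62–153 for Month 3 (SAP 7.7). Assumed: 12 infused subjects and a few moved infusions. The documents give no count or length of delays.

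**1. The SAP's own example.** SAP 7.7 takes a subject who received the IP 5 days after randomization and was assessed at day 65. Study day = 65 − 5 = 60, which lies in 30–61 (Week 6), as the SAP states. The subtracted 5 is the day of actual receipt, so the example uses the protocol's Day 0, not the one in SAP 7.6.

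**2. The same assessment under SAP 7.6.**
- Planned day 3, infused day 5: 65 − 3 = 62, Month 3 window.
- Planned day 7, infused day 5: 65 − 7 = 58, Week 6 window.

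The two definitions can therefore put one observation in different visits.

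**3. Membership.** With Day 0 as the actual infusion date, 12 of 12 infused subjects qualify. With Day 0 as a fixed original date and k moved infusions, 12 − k qualify:
- k = 1: 11 remain, 1/12 = 8.3% lost
- k = 2: 10 remain, 2/12 = 16.7% lost
- k = 3: 9 remain, 3/12 = 25.0% lost

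**4. Effect on the composite event (Clopper-Pearson, 90%).** For 0 of n, the upper limit is 1 − 0.05^(1/n). For 1 of n, the lower limit is 1 − 0.95^(1/n) and the upper limit is the 95th percentile of Beta(2, n − 1).
- The event is in the excluded subject: 1/12 = 8.3% (0.4% to 33.9%) becomes 0/11 = 0% (0% to 23.8%).
- The event is in another subject: 1/12 (0.4% to 33.9%) becomes 1/11 (0.5% to 36.4%).
- No events: the upper limit goes from 22.1% (n = 12) to 23.8% (n = 11).

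Only the first case changes the message, and it needs the moved subject to be the one with the event.

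**5. Week 2 window.** After a delay of d days, a post-infusion sample on the infusion day has study day d, at distance |d − 14| from nominal day 14. A Week 2 visit 14 days after infusion has study day 14 + d, at distance d. For d up to 14 the infusion-day sample is nearer when 14 − d < d, that is d > 7. At d = 15 the distances are 1 and 15, and the Week 2 visit is on day 29, the last day of its window. So for d from 8 to 15 the closest-observation rule would choose the infusion-day sample over the true Week 2 value. This reaches only post-infusion values windowed by day, such as chemistry and hematology. A subject excluded from the Safety Population would show it mainly in ITT or per-protocol outputs.

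**The case against.** A reader might infer that the SAP definitely removes every subject whose infusion was moved. The documents do not support that. The SAP never says that *planned* means the date first scheduled; if a rescheduled date becomes the planned date, every infused subject qualifies. The listings in SAP 8.7 and 8.8 name dates of randomization and IP administration (or attempt) but no separate planned date, so the literal rule could not be programmed from the dates named there.

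Most working rules in the SAP already use actual infusion: the anchor dates in 7.3, baseline in 7.6, both illustrations and the hourly windows in 7.7, and the treatment-emergent definition in 9.2. The SAP also calls itself a supplement to the protocol. *Planned* has a sensible use as well: a CAP-1002 subject who was never infused still needs a Day 0 for ITT study days.

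Two further inferences are weak. The DSMB review holds back enrollment of Group 2, so it does not by itself postpone an infusion already scheduled, and the three-day stagger is known when dates are set. Nor would infusion-day values be misplaced in general: pre-infusion values can still be baseline, serial enzymes and vital signs have hour-based windows, and DSA and the named biomarkers are not drawn that day.

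These points stand, and they make exclusion conditional. They do not remove the conflict. Two definitions in the SAP, one of them governing membership of the primary safety set, differ from the protocol without being declared. That the rest of the SAP uses actual infusion is the reason to correct 7.6.

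**Conclusion.** The point holds in conditional form. It is certain from the text that SAP 7.6 and SAP 6 differ from Protocol 7.2, footnote 1 of the Schedule of Events and Protocol 9.3; that they do not fit SAP 7.3 and the SAP 7.7 example; that the mITT inherits the condition; and that SAP 15 is silent.

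Exclusion of an infused subject is possible but not certain. It requires that an infusion is moved and that *planned* is read as the original date. Each such subject would be 8.3% of an assumed 12 treated. The change from one event to none further assumes that he had the event, and the Week 2 displacement assumes a slip of 8 to 15 days. The only remark on schedule variation is in the Amendment 1 rationale (Protocol Appendix 6), which is background and gives no rate. ITT membership is unaffected. This should be corrected before database lock, because it governs who counts as treated in the primary safety analysis.

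**What to change.** 1. In SAP 7.6, define Day 0 as the actual date of IP infusion for infused subjects; the planned date only for subjects randomized to CAP-1002 and never infused, so that ITT study days can be computed; and the reference day for usual care.
2. In SAP 6, delete *on Day 0* from the active-arm part of the Safety Population so that it matches Protocol 9.3.

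The first change already makes the second redundant, but the deletion is harmless and keeps membership from depending on a date definition. Deleting the phrase alone would not be enough, because study days would still run from the planned day. With both changes, Safety Population membership no longer departs from the protocol and SAP 15 needs no entry for it.

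The cost is two phrases in the SAP, with no new data for any infused subject and no change to study procedures.
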